### 3.4.2 Secondary Efficacy Endpoint(s) and Analyses

### 3.4.2.1 Secondary Efficacy Endpoint(s)

- Change from baseline to the end of dosing at each dose level (Days 7, 14, and 28) in glucose AUC at 24 hours (AUC24h) as measured by CGM
- Change from baseline to the end of dosing at each dose level (Days 7, 14, and 28) in 24-hour mean glucose as measured by CGM
- Change from baseline to the end of dosing at each dose level (Days 7, 14, and 28) in SD of 24-hour glucose readings as measured by CGM
- Change from baseline to Days 7, 14, and 28 in the coefficient of variation (CV) (ratio of SD:mean over 24 hours) of glucose readings as measured by CGM
- Change from baseline to Days 7, 14, and 28 in the mean amplitude of glucose excursion (MAGE) of 24-hour glucose readings as measured by CGM
- Change from baseline to Days 7, 14, and 28 in the percentage of 24-hour glucose readings obtained from CGM that fall within the euglycemic range of ≥ 70 mg/dL (≥ 3.9 mmol/L) and ≤ 180 mg/dL (≤ 10.0 mmol/L)
- Change from baseline to Days 7, 14, and 28 in the percentage of 24-hour glucose readings obtained from CGM that fall within hyperglycemic (high glucose) range of > 180 mg/dL (> 10.0 mmol/L)
- Change from baseline to Days 7, 14, and 28 in the percentage of 24-hour glucose readings obtained from CGM that fall within the hypoglycemic range of < 70 mg/dL (< 3.9 mmol/L)
- Change from baseline to Days 7, 14, and 28 in the percentage of 24-hour glucose readings obtained from CGM that fall within the clinically significant hypoglycemic range of < 54 mg/dL (3.0 mmol/L)

#### 3.4.2.2 Handling of Dropouts and Missing Data

LOCF approach will be used to handle missing data for all secondary efficacy and pharmacodynamics (PD) analyses. If any values used in the calculation of the AUC are missing, the AUC will be calculated as described in the SPP.

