overnight fast for approximately 10 hours. Discharged subjects will return to the clinic on Day 1. Subjects can be randomized after confirming eligibility at any time from Day -1 to Day 1 (predose) to receive either MEDI0382 or placebo. On Day 1, following the overnight fast, dosing of MEDI0382 SC or placebo SC will commence after predose safety measures including but not limited to vital signs, an ECG, and blood collection for laboratory tests (eg, lactate, pH); [REDACTED] dapagliflozin and ketones PK sampling; and measurement of weight are performed. A 24-hour urinary collection for glucose excretion will be collected from Day 1 to Day 2. Subjects will be monitored for safety, glucose, and ketones, and will be discharged from the unit approximately 6 hours postdose. Capillary glucose and ketones monitoring will be done at the site using a glucometer. The subject will return to the unit on Day 2 for safety monitoring and supervision of investigational product administration. The subjects will be discharged with the same syringe pack of investigational product supplies and will continue to self-administer investigational product on an outpatient basis.

[figure not shown]
Subjects will then return to the clinical unit at weekly intervals until a maintenance dose of 300 µg is achieved. Subjects will return to the unit for outpatient visits on Days 7, 8, 14, 15, and 22 to undergo safety assessments including but not limited to an abbreviated physical examination and ECG (Days 7, 14, and 22), vital signs (all visits with ABPM fitted on Day 14 only), urine tests (eg, pregnancy test on Day 14 and Day 22), and blood collection for laboratory tests (Days 7, 14, and 22). MEDI0382, dapagliflozin, and ketones PK sampling will be performed on Days 7, 8, 14, and 15. Uptitration of SC investigational product will occur on Day 8 and Day 15. After uptitration of investigational product, subjects will be monitored for safety, capillary glucose and ketones and will be discharged 6 hours postdose. A 10-hour overnight fast is required prior to visits on Days 7 and 14, and a standardized breakfast meal will be provided 2 hours postdosing on these days. The CGM device will be replaced on Day 14.

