#### 3 STATISTICAL METHODS

#### 3.1 General Considerations

Data will be presented in data listings sorted by treatment group, subject number, and date collected, where appropriate. Tabular summaries will be presented. Categorical data will be summarized by the number and percentage of subjects within each category. In general, continuous variables will be summarized by descriptive statistics including mean, standard deviation, median, minimum, and maximum. For some variables, the geometric mean and 95% CI will be presented.

All available data will be included in the analyses and missing data will not be imputed, except in a last observation carried forward (LOCF) analysis and as specified in the

calculation of the AUC values. When LOCF is used to impute for missing post-baseline data, only post-baseline data will be carried forward (eg, baseline data will not be carried forward). Unless otherwise specified, baseline values will be defined as the last valid assessment prior to the first administration of study medication (MEDI0382 or placebo).

All statistical tests will be 2-sided at an alpha level of 5% unless stated otherwise. There will be no adjustment for multiplicity.

Data analyses will be performed using SAS® version 9.3 or higher (SAS Institute Inc., Cary, NC). The analytical results generated from SAS programs will follow MedImmune SAS programming standards and will be validated according to MedImmune SAS validation procedures.

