#### 3.4.2.3 Secondary Efficacy Analyses

Secondary efficacy analysis will be based on the ITT population. The secondary efficacy endpoints will be summarized by treatment group at each time point and analyzed similarly to the analysis of primary efficacy endpoint with LOCF approach to handle missing data.

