### 3.4.3 Exploratory Efficacy Endpoint(s) and Analyses

#### 3.4.3.1 Exploratory Efficacy Endpoint(s)

- Change from baseline (Day -1) to Day 28 in FPG
- Change from baseline (Day -2) to Day 28 in HbA1c
- Change from baseline (Day 1) to Day 29 in body weight (kg)
- Percentage change from baseline (Day 1) to Day 29 in body weight (kg)
- Proportion of subjects achieving  $\geq$  5% body weight loss from baseline (Day 1) to Day 29

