### 3.4.3.2 Exploratory Efficacy Analyses

Exploratory efficacy analyses will be based on the ITT population. The change from baseline endpoints will be summarized by treatment group at each time point and the final treatment evaluation time analyzed similar to the analysis of primary efficacy endpoint with LOCF approach to handle missing data.

The proportion of subjects achieving  $\geq 5\%$  body weight loss from baseline (Day 1) to Day 29 will be analyzed using a logistic regression by adjusting baseline value and treatment group.

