### 3.5.1.2 Analysis of Pharmacodynamic Endpoint(s)

PD analysis will be based on the ITT population. The change from baseline endpoints for GLP-1, glucagon, insulin, and c-peptide AUC0-4h and for fasting FFA levels will be summarized by treatment group at each time point and the final treatment evaluation time analyzed similar to the analysis of primary efficacy endpoint with LOCF approach to handle missing data.

Descriptive statistics will be provided for  $\beta$ -hydroxybutyrate parameters: AUC0-inf, AUC0-last, Cmax, and tmax at each time point and total glucose urinary excretion (Days 1 and 28). The  $\beta$ -hydroxybutyrate parameters will be calculated by the Pharmacokinetics group following the calculations provided below in the Pharmacokinetics Section.

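### LOCF lets a 100 or 200 µg value stand as the Day 28 result for fasting FFA and FPG, and possibly as the Day 14 or Day 28 result for CGM

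*SAP*

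**What the plan says.** - **CGM (secondary).** SAP 3.4.2.2: "LOCF approach will be used to handle missing data for all secondary efficacy and pharmacodynamics (PD) analyses". SAP 3.4.2.3 has these endpoints "analyzed similarly to the analysis of primary efficacy endpoint with LOCF approach to handle missing data". Three of the nine CGM endpoints are tied to dose, for example "Change from baseline to the end of dosing at each dose level (Days 7, 14, and 28) in glucose AUC at 24 hours". The other six name the same three days without mentioning dose.
- **Fasting FFA (PD).** SAP 3.5.1.2 has "the final treatment evaluation time analyzed similar to the analysis of primary efficacy endpoint with LOCF approach".
- **FPG (exploratory).** The endpoint is "Change from baseline (Day -1) to Day 28 in FPG". SAP 3.4.3.2: "The change from baseline endpoints will be summarized by treatment group at each time point and the final treatment evaluation time analyzed similar to" the primary analysis, again with LOCF.
- **Limit on carrying.** SAP 3.1 allows that "only post-baseline data will be carried forward (eg, baseline data will not be carried forward". It sets no limit by dose level.
- **Titration.** Protocol 3.1.1: "Uptitration of SC investigational product will occur on Day 8 and Day 15". Day 7 is therefore at 100 µg, Day 14 at 200 µg and Day 28 at 300 µg.
- **Source of the rule.** The protocol asks for LOCF in the Synopsis and in 4.8.3.1 to 4.8.3.3. SAP 3.4.1.2 has already dropped it for the primary endpoint, which has only one post-baseline value.

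**The concern.** LOCF treats the last available value as a stand-in for the missing one. Under forced titration the stand-in may come from a lower dose. A Day 28 contrast, or one defined as the last day at a given dose level, could then contain data from before that dose was reached, and the SAP sections provided neither report this nor test its effect.

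Missing values are plausible. A subject may stay in the study without a sensor (Protocol 4.3.6.1), and sensors can fail (Protocol Table 4.2.3-1, footnote w). Earlier 300 µg cohorts had nausea in up to 41.7% and vomiting in up to 27.3% of subjects (Protocol 3.2.3.2), so loss could be greater on active treatment. At stake is how the secondary CGM and exploratory FFA and FPG contrasts are read.

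**Working it through.** **1. The plan's own figure.** The only power statement concerns the primary endpoint. Both effects are 1.5 SD (30/20 and 225/150). With 23 per arm, the noncentrality is 1.5/√(2/23) = 5.09 on 44 df. Two-sided 5% power is 99.9%, consistent with the stated > 95%. It does not depend on LOCF. The plan gives no figure for CGM, FFA or FPG.

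**2. Where a carried value can come from** (Protocol Table 4.2.3-1).

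| Endpoint | Treatment-period values | Missing day | Possible source |
|---|---|---|---|
| FFA, FPG | Days 7, 14, 28 | 28 | Day 14 (200 µg) or Day 7 (100 µg) only |
| CGM, if only analysis days count | Days 7, 14, 28 | 14 | Day 7 (100 µg) |
| | | 28 | Day 14 (200 µg) or Day 7 (100 µg) |
| CGM, if any 24-hour window counts | daily | 14 | Days 8-13 (200 µg), if recorded |
| | | 28 | Days 15-27 (300 µg), if recorded |
| HbA1c, MMTT hormones | Day 28 | 28 | nothing to carry |

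The readable items of the early-discontinuation visit (Protocol 4.2.4.1) include neither FFA nor FPG. Day 22 serum chemistry includes glucose, but that visit does not require an overnight fast and FPG is a separate schedule line.

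**3. Size, by proxy.** Let f be the fraction carried in each arm and Δ the change in that arm's mean from the carried day to the target day. The shift in active minus placebo is −f_active·Δ_active + f_placebo·Δ_placebo. If placebo is flat and the lower dose has a share r of the 300 µg effect, the contrast shrinks by f(1 − r).

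The share r comes from earlier MMTT glucose AUC results:

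- 200 µg (Protocol 1.4): −32.78 + 10.16 = −22.62 points.
- 300 µg (Protocol 3.2.1.2), ranges paired as printed: −36.73 + 8.02 = −28.71 and −41.65 + 14.54 = −27.11.
- 300 µg, paired the other way: −36.73 + 14.54 = −22.19 and −41.65 + 8.02 = −33.63.
- Ratios: 22.62/28.71 = 0.788; 22.62/27.11 = 0.834; 22.62/22.19 = 1.02 (taken as 1.0); 22.62/33.63 = 0.673.

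Shrinkage of a Day 28 contrast when Day 14 is carried, for an assumed 10-30% random loss in the active arm (about 2 to 7 of 23):

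| r | f = 0.1 | f = 0.2 | f = 0.3 |
|---|---|---|---|
| 0.673 | 3.3% | 6.5% | 9.8% |
| 0.788 | 2.1% | 4.2% | 6.4% |
| 0.834 | 1.7% | 3.3% | 5.0% |
| 1.0 | 0 | 0 | 0 |

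A simulated ANCOVA agrees with the formula. With true effects of −20 (Day 14) and −30 (Day 28) and 20% against 5% missing, LOCF gave −28.04 and full data −30.05; the formula predicts a shift of 0.2 × 10 = 2.0. For carry from Day 7 the documents give no 100 µg figure. An assumed 100/200 ratio of 0.5-1.0 gives 0-15% at Day 14, and an assumed 100/300 ratio of 0.33-1.0 gives 0-20% at Day 28.

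**4. Does a repeated-measures model do better?** The simulation used 23 per arm, a Day 28 effect of 1.5 SD, an assumed visit correlation of 0.6, and active-arm loss of 10-30% after Day 14.

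- Random loss: the model is essentially unbiased, with a sampling SD 1-10% above LOCF. At r = 1.0, or at 0.81, there is no net gain in root-mean-square error.
- Poorer Day 14 responders lost, r = 0.673: LOCF understates by about 6-15%; the model stays within about 0.5%.
- Loss depending on the unseen Day 28 value, r = 0.673: the model overstates by about 4-13%, and LOCF understates by 0.6-3.6%.

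**5. If leavers keep no effect** (assumed). The true contrast by randomized group is then (1 − f) of the full effect. At r = 0.673, LOCF gives [1 − f(0.327)]/(1 − f): 0.967/0.9 = 1.07 at f = 0.1 and 0.902/0.7 = 1.29 at f = 0.3. The model gives 1/(1 − f): 1.11 and 1.43. Both overstate, the model by more.

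**The case against.** The strongest reply is that bias needs a target and the SAP names none. The shrinkage figures take as truth that every active subject has the full Day 28 effect. That suits a lost sensor. It suits FFA and FPG less well, because Protocol 4.1.6 keeps most subjects who stop product under observation, so missing values come largely from those who leave. Step 5 shows that the ranking of methods can then reverse. This stands, and it is why the fix must state the quantity estimated.

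Three further points stand:

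- The CGM part is conditional. With readings every 15 minutes and failed sensors replaced as soon as possible, a same-dose window may often exist. The statistical programming plan, which was not available, may define it.
- The proxy is weak. It compares a 200 µg cohort treated for up to 41 days with cohorts given 300 µg for 7 days, so dose and duration are confounded, and it uses postprandial glucose.
- Body weight is also under LOCF and is measured at early-discontinuation visits. It is not sized here.

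None of this removes the basic fact. For FFA and FPG, any value carried to Day 28 predates the last dose step.

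**Conclusion.** The point holds as a permitted mixing of dose levels. It is certain for any carried Day 28 FFA or FPG value, and conditional on the meaning of last observation for CGM. A plausible size for a Day 28 glucose contrast is 0-10% shrinkage, given Day 14 carry, 10-30% random loss in the active arm, a flat placebo response and an MMTT-based ratio of 0.67-1.0.

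A reader might infer more than the documents support:

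- *That LOCF necessarily biases these contrasts toward zero.* There is no missing rate and no dose-response for CGM, FFA or FPG. The bias may be nil, it may reverse for leavers, and no direction can be stated for FFA.
- *That the trial's main result is at risk.* The primary endpoint is not imputed (SAP 3.4.1.2).
- *That a repeated-measures model isolates the 300 µg effect.* Analysis is by randomized group, off-product data may be included, and forced titration ties dose to time.

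Priority is low to moderate. The endpoints are secondary or exploratory in an exploratory Phase 2a study, but the remedy is cheap.

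**What to change.** 1. State that no value is carried across the Day 8 or Day 15 dose step. For CGM, define the 24-hour analysis window and allow a missing analysis day to be filled only from an earlier window at the same dose level.
2. For the seven CGM endpoints other than the two hypoglycemia percentages, and for fasting FFA and FPG, make the main analysis a repeated-measures model on observed Day 7, 14 and 28 data: treatment, visit, treatment-by-visit, baseline and baseline-by-visit. Name available-case ANCOVA as the fallback. State the quantity estimated, including how values from subjects off product are treated.
3. For the percentages of readings below 70 and below 54 mg/dL, summarize observed data without carry-forward and name one comparison in advance.
4. Keep LOCF only as a labelled sensitivity analysis, as an exception to item 1. For FFA and FPG, the label should say that every value carried to Day 28 comes from a lower dose. Tabulate carried values by arm and visit.
5. Record the departure from the LOCF wording in the Protocol Synopsis and 4.8.3.1 to 4.8.3.3.

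The cost is SAP wording, one standard SAS procedure and the recorded departure. The downsides are a missing-at-random assumption, slightly lower precision, no gain if the effect is flat across doses, and possible overstatement if loss depends on the unseen Day 28 value or if leavers lose the effect. The ANCOVA fallback ignores earlier visits, so it can also overstate if poorer Day 14 responders are lost.

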#### 3.4.2.3 Secondary Efficacy Analyses

Secondary efficacy analysis will be based on the ITT population. The secondary efficacy endpoints will be summarized by treatment group at each time point and analyzed similarly to the analysis of primary efficacy endpoint with LOCF approach to handle missing data.

### 3.4.3 Exploratory Efficacy Endpoint(s) and Analyses

#### 3.4.3.1 Exploratory Efficacy Endpoint(s)

- Change from baseline (Day -1) to Day 28 in FPG
- Change from baseline (Day -2) to Day 28 in HbA1c
- Change from baseline (Day 1) to Day 29 in body weight (kg)
- Percentage change from baseline (Day 1) to Day 29 in body weight (kg)
- Proportion of subjects achieving  $\geq$  5% body weight loss from baseline (Day 1) to Day 29

### 3.4.3.2 Exploratory Efficacy Analyses

Exploratory efficacy analyses will be based on the ITT population. The change from baseline endpoints will be summarized by treatment group at each time point and the final treatment evaluation time analyzed similar to the analysis of primary efficacy endpoint with LOCF approach to handle missing data.

The proportion of subjects achieving  $\geq 5\%$  body weight loss from baseline (Day 1) to Day 29 will be analyzed using a logistic regression by adjusting baseline value and treatment group.

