1.4 Summary of Clinical Experience

In prior clinical experience with MEDI0382 (Cohort 4 of Study D5670C00002), 51 overweight and obese subjects with T2DM were randomized to receive MEDI0382 titrated up from a starting dose of 100 µg to a dose of 200 µg or placebo for up to 41 days. MEDI0382 was shown to have a similar tolerability to marketed GLP-1 receptor agonists, with no significant increases in systolic or diastolic BP observed. Following a mixed-meal tolerance test (MMTT), a least squares (LS) mean for percent change from baseline in glucose area under the concentration-time curve from 0 to 4 hours (AUC_{0-4h}) of -32.78%

(90% confidence interval [90% CI] -36.98, -28.57) was observed in MEDI0382-treated subjects versus -10.16% (90% CI -14.10, -6.21) in placebo-treated subjects ($p < 0.0001$). A LS mean change from baseline in body weight of -3.84% (90% CI -4.55, -3.12) was observed in MEDI0382-treated subjects versus -1.70% (90% CI -2.40, -1.01) in placebo-treated subjects ($p < 0.001$). In the same study (D5670C00002), doses of 300 μg were studied for 7 days in 2 separate cohorts, each exploring different uptitration schedules to reach this dose. The tolerability and efficacy profiles were similar to that observed in previous cohorts.

The combination of MEDI0382 with dual therapy of dapagliflozin and metformin has not been studied previously. However, given the commercial availability of dapagliflozin, this drug (and other SGLT2 inhibitors) will likely be a concomitant medication in future Phase 3 clinical studies of MEDI0382. Because the 2 agents exert their glyceemic and weight-lowering effects via different mechanisms, the coadministration of the 2 compounds is expected to show improved effects on glyceemic control and body weight as well as positive effects on BP (due to renal sodium loss driven by both SGLT2 inhibition and glucagon) compared to the oral, dual therapy of dapagliflozin and metformin given alone.

Given the likelihood of concomitant administration of MEDI0382 with SGLT2 inhibitors and metformin in the ongoing clinical development program, this exploratory study aims to (a) explore the efficacy and safety profile associated with the combination of MEDI0382 and dual therapy of SGLT2 inhibitor (dapagliflozin) and metformin and (b) characterize the profile of glyceemic and metabolic control following administration of the triple combination therapy versus oral, dual-combination therapy.

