1.6.2 Hypoglycemia

A hypoglycemic event is considered severe if associated with severe cognitive impairment requiring external assistance for recovery as defined by the American Diabetes Association. Spontaneous and clinically significant hypoglycemia defined as blood glucose < 54 mg/dL [3.0 mmol/L] with or without symptoms ([Skyder et al, 2017](#)) has not been seen in prior studies with MEDI0382 (up to a dose of 300 µg) alongside metformin. In addition, no episodes of major and minor hypoglycemia were reported in a randomized control study evaluating the efficacy and safety of exenatide (a GLP-1 monoagonist) in combination with dapagliflozin on a background of metformin ([Frías et al, 2016](#)). Furthermore, the mechanism of action of dapagliflozin (SGLT2 inhibition) does not interfere with normal endogenous glucose production in response to hypoglycemia and does not stimulates insulin release. Therefore, the risk of hypoglycemia in this study is considered low. However, all subjects will be provided with a diary and a glucometer and will be advised to check their capillary blood glucose level if they have symptoms of hypoglycemia (hunger, dizziness, shaking, sweating, or irritability) or feel unwell and will be expected to record the blood glucose level in their diary and contact the study team immediately. Management of the event should be as per standard local protocols. Hypoglycemia episodes should be documented as an adverse event (AE). Pharmacological treatments administered for hypoglycemia (eg, dextrose/glucose tablets, glucagon) should be recorded in the electronic case report form (eCRF) as concomitant medications.

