3.2.1.2 MEDI0382

To date, the development program for MEDI0382 has studied doses up to 300 µg as part of a multiple ascending dose study (D5670C00002). The 300 µg dose has been specifically studied for a period of 7 days in 2 separate cohorts, each exploring different uptitration schedules to reach this dose. At the 300 µg dose level, the safety and tolerability profile was comparable with previous clinical data with lower doses of MEDI0382 and other GLP-1 mimetics at this stage of development, and there was no increase in systolic or diastolic BP. In fact, a nonsignificant trend towards reduction of systolic BP was observed (~2-5 mmHg reduction across the cohorts after data correction for placebo). Across the 2 cohorts, the LS mean for percent change from baseline to the end-of-treatment period in glucose AUC_{0-4h}

following a MMTT was -36.73% to -41.65% in MEDI0382-treated subjects versus -8.02% to -14.54% in placebo-treated subjects. The LS mean for change from baseline in body weight was -2.07% to -3.40% in MEDI0382-treated subjects versus -0.68% to -0.86% in placebo-treated subjects. Of note, no events of DKA have been observed in the MEDI0382 development program to date.

The current study intends to minimize the likelihood of observing adverse effects by titrating MEDI0382 up to 300 µg (ie, the highest dose previously tested). In addition, this study ensures that all doses that are likely to be included in later stages of MEDI0382 development (ie, 100 µg through 300 µg) are studied in combination with dapagliflozin.

Similar studies conducted with exenatide in combination with dapagliflozin showed no significant impact on the PK of either drug in the combination arm, despite the delay in gastric emptying due to the GLP-1 component of exenatide. Furthermore, given the earlier time to maximum-observed serum drug concentration (t_{max}) of dapagliflozin (~1 hour) compared to MEDI0382 (~4 hours), the potential for additional delay in gastric emptying due to the glucagon component of MEDI0382 is not deemed to be relevant to the absorption phase of dapagliflozin. Therefore, it is expected that MEDI0382 and dapagliflozin will retain their typical PK profile in the presence or absence of the coadministered drug.

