### 2.3 Treatment Assignment and Blinding

An Interactive voice/web response system (IXRS) will be used for assignment of dapagliflozin tablet bottles (where required), randomization to a treatment group, and assignment of blinded MEDI0382 or placebo investigational product kit numbers. A subject is considered randomized into the study when the investigator notifies the IXRS that the subject meets eligibility criteria, and the IXRX provides the assignment of investigational product kit number to the subject.

Eligible subjects will be randomized at a 1:1 ratio following screening to receive either MEDI0382 SC or placebo SC. The IXRS will assign a unique randomization code and treatment group to the subject at each randomization. Subjects who withdraw from the study may be replaced, if deemed necessary by the medical monitor, to ensure that safety data are collected on a sufficient number of subjects.

This is a double-blind study in which MEDI0382 and placebo are not identical in the prefilled syringe titration volumes. Neither the subject nor any of the investigator or sponsor staff who are involved in the treatment or clinical evaluation of the subjects will be aware of the treatment received (ICH E9).

The different fill volumes of investigational product (MEDI0382 and placebo) and the relative position of the plunger rods will be visually distinct during administration. To maintain the blind, investigational product (MEDI0382 and placebo) prefilled syringes will be handled by an unblinded investigational product manager or unblinded study personnel that will not be involved in the treatment or clinical evaluation of subjects. An unblinded qualified designee may administer investigational product to subjects during in-clinic visits.

An independent investigational product monitor will also be unblinded to perform investigational product accountability. In the event that a treatment allocation for a subject becomes known to the investigator or other study staff involved in the management of study subjects, the sponsor must be notified immediately. If the treatment allocation for a subject needs to be known to treat an individual subject for an adverse event (AE), the investigator must notify the sponsor immediately. The site will maintain a written plan detailing which staff members are blinded/unblinded and the process of investigational product administration used to maintain the blind.

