### 2.4 Sample Size

A total of 46 subjects are planned for the study. Each of the 2 treatment groups will be randomized at a 1:1 ratio to receive (a) MEDI0382 with dapagliflozin and metformin administered simultaneously or (b) placebo with dapagliflozin and metformin administered simultaneously. A sample size of 23 subjects in each treatment group will provide a study power > 95% to detect a difference of 30% between treatment groups in relative change from baseline in glucose AUC0-4h at a two-sided alpha of 5%, assuming a common standard deviation (SD) of 20%. This sample size will also provide a study power > 95% to detect a difference of 225 hr•mg/dL between treatment groups in absolute change from baseline in glucose AUC0-4h at a two-sided alpha of 5%, assuming a common SD of 150 hr•mg/dL. The SD assumptions are based the result of 300 μg cohorts in a prior study (D5670C00002).

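### The logistic regression for at least 5% weight loss has roughly a 25–63% chance of meeting a placebo arm with no responders, where it gives no finite odds ratio, and the SAP names no alternative

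*SAP*

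**What the plan says.** SAP 3.4.3.2 gives one method for the proportion of subjects losing at least 5% of body weight from Day 1 to Day 29: it "will be analyzed using a logistic regression by adjusting baseline value and treatment group". Protocol 4.8.3.3 names the same model. Neither document says which test is to be read from the model, gives an exact or penalized alternative, or says what is reported if the odds ratio cannot be estimated. SAP 3.1 adds "All statistical tests will be 2-sided at an alpha level of 5% unless stated otherwise", without multiplicity adjustment.

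The sample size was set for the glucose endpoints. SAP 2.4 states "A sample size of 23 subjects in each treatment group will provide" more than 95% power for those, and says nothing about responders.

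The documents state neither an expected responder rate nor an SD for weight change. They do give earlier means:

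- Protocol 1.4, Cohort 4 (51 randomized, up to 41 days): -3.84% (90% CI -4.55 to -3.12) on MEDI0382 and -1.70% (-2.40 to -1.01) on placebo.
- Protocol 3.2.1.2, two 300 µg cohorts: -2.07% to -3.40% on MEDI0382 and -0.68% to -0.86% on placebo.

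**The concern.** Few placebo subjects are likely to lose 5% of their weight in 28 days, and an arm of 23 may contain none. If one arm has no events, the treatment coefficient has no finite maximum-likelihood estimate (separation). The software reports a very large odds ratio, with a standard error that reflects only where the iterations stopped. The Wald p-value is then close to 1 however many responders the other arm has. A likelihood-ratio test from the same model still gives a finite p-value.

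Because the SAP names neither test, the choice would be made after the data are seen, and it could decide whether the result reads as clear evidence or none.

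**Working it through.** **The plan's own figure.** The power statement concerns the primary endpoints. With 23 per arm, 30 / (20 × √(2/23)) = 5.09, so power is about Φ(5.09 − 1.96) = 0.999. The absolute endpoint has the same ratio (225/150 = 30/20). The claim of more than 95% reproduces. There is no corresponding figure for responders.

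**Step 1: SD of % weight change.** SD = half-width / t(0.95, 48 df) × √n, with t = 1.677 and an assumed split of the 51 subjects into 25 and 26.

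- MEDI0382: half-width (4.55 − 3.12)/2 = 0.715, so SD = 0.715/1.677 × √25 = 2.13.
- Placebo: half-width (2.40 − 1.01)/2 = 0.695, so SD = 0.695/1.677 × √26 = 2.11.

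I use 2.1.

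**Step 2: responder rates.** Under normality, p = Φ((−5 − mean)/2.1).

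- Placebo: 5.8% at −1.70, 2.4% at −0.86, 2.0% at −0.68. That is 1.3, 0.6 and 0.5 expected responders in 23.
- MEDI0382: 29% at −3.84, 22% at −3.40, 8% at −2.07. That is 6.7, 5.1 and 1.9 expected responders.

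**Step 3: probability of separation.** P(no placebo responder) = (1 − p_placebo)^23, multiplied by P(at least one MEDI0382 responder) = 1 − (1 − p_active)^23.

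| Means, active vs placebo | No placebo responder | At least one active responder | Product |
|---|---|---|---|
| −3.84 vs −1.70 | 25% | >99% | 25% |
| −3.40 vs −0.86 | 57% | >99% | 57% |
| −3.40 vs −0.68 | 63% | >99% | 63% |
| −2.07 vs −0.68 | 63% | 86% | 54% |

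In the last row a further 9% or so of trials have no responder in either arm, which also leaves the treatment effect inestimable.

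**Step 4: sensitivity to the SD.** Across these pairings the product runs from about 10% (SD 2.5, −3.84 vs −1.70) to 76% (SD 1.9, −3.40 vs −0.68).

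**Step 5: with the baseline covariate in the model.** In 2,000 simulated trials per scenario (baseline weight assumed to have mean 95 kg and SD 16, unrelated to response), separation occurred in 25%, 55%, 63% and 68% of trials, in the order of the table. The last figure includes about 10% with no events at all. The covariate does not remove the problem.

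**Step 6: what the output would look like.** Take 6/23 versus 0/23, close to the expected active count in the first two rows.

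- Wald test: SE about 16,600, p = 0.999.
- Fisher's exact test: p = 0.022.
- Likelihood-ratio test, unadjusted: 2 × {[6 ln(6/23) + 17 ln(17/23)] − [6 ln(6/46) + 40 ln(40/46)]} = 9.22 on 1 df, p = 0.0024.
- Firth, unadjusted (half an event added per cell): odds ratio (6.5/17.5)/(0.5/23.5) = 17.5. The penalized log-likelihood is 6.5 ln(6.5/24) + 17.5 ln(17.5/24) + 0.5 ln(0.5/24) + 23.5 ln(23.5/24) = −16.45, and without treatment 7 ln(7/48) + 41 ln(41/48) = −19.94. Twice the difference is 6.98, p = 0.008.

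The same data therefore give p-values from about 0.002 to 0.999, according to a choice the SAP leaves open.

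**The case against.** **The probabilities are derived, not stated.** This stands as a limit on precision. They need normality, the 25/26 split, and transfer of the Cohort 4 SD to the 300 µg cohorts. If the least squares means came from a covariate-adjusted model, 2.1 is a residual SD and the raw SD would be larger. Cohort 4 ran for up to 41 days against 28 here, which favors fewer placebo responders now. All subjects here also take dapagliflozin, which Protocol 1.1 links to weight loss, and this could mean more. Even at SD 2.5 the risk is 10–37%.

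**A real effect would not necessarily be lost.** A reader might infer that an excess of responders would be reported as non-significant. That follows only from a Wald test, which the SAP does not specify. Counts and percentages by arm are tabulated anyway, so 6 versus 0 would be visible. What remains is an unspecified test and an odds ratio without a finite value.

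**The endpoint is minor.** It is one exploratory dichotomy in an exploratory Phase 2a study, and change and % change in weight are analyzed by ANCOVA. Detailed specifications also sit in a statistical programming plan that is not among the documents, so a fallback there cannot be excluded.

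**The argument might seem to reach the CGM endpoints too.** A reader might infer that the protocol's figures also predict failure of the ANCOVA for % of readings below 54 mg/dL, which SAP 3.4.2.3 has "analyzed similarly to the analysis of primary efficacy endpoint". The documents do not support that. No CGM rate is given. Protocol 1.6.2 says such hypoglycemia "has not been seen in prior studies with MEDI0382" alongside metformin, but this refers to blood glucose, not to interstitial readings every 15 minutes (96 a day). Few non-zero values is only a plausible expectation. If a fraction q of subjects has any such reading, all 46 values are zero with probability 0.99^46 = 63% at q = 1%, but 0.95^46 = 9% at 5% and 0.90^46 = 0.8% at 10%, with q assumed throughout. The ANCOVA is undefined only if every change is zero. Nor is a Fisher test a cure, since its type I error at q = 5% is about 0.3%. Capillary values below 54 mg/dL are recorded as adverse events in any case (Protocol 4.3.6.2).

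**Conclusion.** The point holds for the weight-responder model only. At an SD of about 2.1, the planned maximum-likelihood logistic regression has about a 25–57% chance of separation, 63% for −3.40 versus −0.68, and about 10–76% over SDs of 1.9–2.5. These figures rest on the assumptions in steps 1 and 2. When separation occurs there is no finite odds ratio, the default Wald test carries no information, and the SAP does not say what replaces it.

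The gap is worth closing because closing it costs almost nothing, but little depends on it and the primary analysis is unaffected. It does not extend to a claim that the CGM ANCOVA will fail.

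**What to change.** In SAP 3.4.3.2, replace ordinary maximum-likelihood logistic regression with Firth-penalized logistic regression on baseline weight and treatment, reporting the odds ratio with a profile-likelihood confidence interval and a penalized likelihood-ratio p-value. Also report responder counts and the risk difference with an exact or score interval, with Fisher's exact test as the unadjusted check. State that if neither arm has a responder, only the counts and the interval for the risk difference are given.

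The cost is a few lines of SAP text and standard software options. The Firth estimate is slightly shrunk, and Fisher's test drops the baseline adjustment. Exact logistic regression should not be the first choice: with a continuous baseline weight and few events, its conditional distribution can degenerate until significance is unreachable.

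Optionally, for CGM readings below 54 mg/dL, add a descriptive count by arm of subjects with any reading in range.
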